# 4.4 Other endpoints analyses

For the other endpoints, no data collected after treatment discontinuation are used.

Type of document Document ID	Date: Version: Status:	11-Aug-2022 4.0 Final	
INTERNAL USE	Page:	37 of 79	

# 4.5 Safety analyses

All safety tables and listings will be for the safety analysis set unless otherwise specified.

#### 4.5.1 Extent of exposure

#### 4.5.1.1 Tablets taken

The number of tablets taken is calculated as the difference between the number of tablets dispensed and the number of tablets returned or lost.

The number of tablets taken will be summarised by treatment group.

#### 4.5.1.2 Treatment duration

The duration of treatment for each subject is calculated from the date of randomisation up until (and including) the date of last IMP intake. The period may include interruptions.

Treatment duration will be summarised by treatment group.

#### 4.5.1.3 Treatment days and treatment year

Treatment days is the number of tablets taken. A treatment year is the number of tablets taken divided by 365.

Treatment days and treatment years will be displayed in summary tables by treatment groups.

#### 4.5.1.4 Compliance

Compliance will be calculated for each subject as the number of tables taken divided by the treatment duration in days and multiplied with 100.

Percentage compliance will be summary by treatment group.

Type of document	Date:	11-Aug-2022	
Document ID	Version:	4.0	
	Status:	Final	
INTERNAL USE	Page:	39 of 79	

# 4.5.2 AEs

AEs are recorded from the subjects sign the informed consent and until the last follow-up visit.

Treatment-emergent adverse events (TEAEs) are defined as AEs with start time on or after the time of first IMP administration and no later than 7 days after the last day of IMP administration. If, due to partial time/dates, there is any doubt whether an AE is treatment-emergent, the event will conservatively be assessed as treatment-emergent.

Non-TEAEs are AEs that occur prior to first IMP administration or more than 7 days after last IMP administration.

IMP-related AEs are TEAEs that are assessed 'possibly related' or with missing assessment.

Severe and clinically relevant asthma exacerbations reported during the trial are expected as a result of subjects' background disease and will be evaluated as part of the primary endpoint. Adverse events are separated into three groups: solicited AEs, clinically relevant asthma exacerbations and other events including events synonymous with solicited terms and present after the soicitation period.

All TEAEs and all IMP-related AEs will be summarised by treatment group, MedDRA System Organ Class (SOC) and Preferred Term (PT) displaying number of subjects in treatment group, number and percentage of subjects having the event as well as number of events.

All TEAEs and IMP-related AEs will be broken down by intensity (mild, moderate, severe), seriousness, action taken and outcome and summarised by treatment group displaying number of subjects in treatment group, number and percentage of subjects having the event as well as number of events.

Number of events and number and percentage of subjects having TEAEs of special interest will be displayed in summary tables. The events of special interest will be based on the investigator's assessment of an event being "an anaphylactic reaction, an anaphylaxis and/or a systemic allergic reaction"; "an event treated with adrenaline/epinephrine"; "severe local swelling or oedema of the mouth and/or throat" or "an eosinophilic oesophagitis" along with SAEs of severe asthma exacerbations and clinically relevant asthma exacerbations.

Number of events and number and percentage of subjects having local application site TEAEs; medication error; drug abuse, misuse and overdose based on investigators assessments in the eCRF, will also be displayed in summary tables.

TEAEs leading to IMP interruptions, serious TEAEs (SAEs) and TEAEs leading to IMP discontinuations will be summarised by SOC, PT and treatment group in separate tables. A cumulative incidence plot will be used to show the cause specific distribution of IMP discontinuation due to TEAEs.

Most frequent TEAEs are those AEs (defined as MedDRA PTs) that are present in at least 2% of subjects with active treatment. Most frequent TEAEs and most frequent IMP-related AEs will be summarised by SOC, PT and treatment group in separate tables.

Additionally, the following TEAEs will be summarised by treatment group displaying the number and frequency of subjects having the event as well as number of events, see **0** (Appendix 3: Preferred Terms):

- asthma related events
- asthma related hospitalisations

Type of document	Date:	11-Aug-2022	
Document ID	Version:	4.0	
	Status:	Final	
INTERNAL USE	Page:	40 of 79	

Κ

- worsening of asthma requiring medication
- asthma related symptoms leading to IMP discontinuation
- solicited TEAEs
- TEAEs excluding solicited events and clinically relevant asthma exacerbations

Onset of a TEAE is defined as time (e.g. minutes or days) from first IMP intake to start of the first TEAE of a given PT. An onset of 1 day means that the TEAE has started on the day of first IMP intake.

Resolution time of a TEAE is defined as days from start of the TEAE until the TEAE is resolved, e.g., recurrent TEAEs like oral pruritus that occurs every day for 1 minute on 5 days in a row will have a resolution time of 5 days.

Resolution time and onset in minutes/hours/days will be summarised by treatment group for most frequent TEAEs and for local application site TEAEs displaying mean, SD, median, 5% percentile, 95% percentile, minimum and maximum.

For solicited TEAEs the duration in minutes on the first day of IMP intake will be summarised.

All AEs will be listed including non-TEAEs.

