5.1 Discontinuation from IMP treatment

Subjects must be discontinued from IMP treatment and should continue in the trial for safety assessments only under the following circumstances:

- If the subject experiences 2 severe asthma exacerbations within a 12 consecutive months period
- If the subject is hospitalised due to asthma requiring treatment with systemic corticosteroids
- The subject experiences severe or persistent symptoms of oesophagitis
- If the subject becomes pregnant
- If, in the investigator's opinion, continuation with IMP treatment would be detrimental to the subject's well-being

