15.9 Safety analyses

Analyses of AEs

AEs are recorded from the subjects sign the informed consent and until the last follow-up visit.

Unless otherwise specified, AE endpoints in this protocol refer to events occurring after the first IMP administration (treatment-emergent AEs).

AEs will be summarised by treatment group, MedDRA system organ class (SOC) and preferred term (PT) displaying number of subjects in treatment group, number and percentage of subjects having the event as well as number of events. Furthermore, the AEs will be summarised according to severity, relationship, outcome and seriousness.

Additionally the following AEs will be summarised by treatment group

- asthma exacerbations
- asthma related hospitalisations
- worsening of asthma requiring medication
- discontinuations of treatment due to asthma related symptoms
- solicited AEs
- unsolicited adverse events

The analyses will be described further in the SAP.

Analyses of other safety parameters

Physical examination assessments, laboratory assessments, vital signs and FEV_1 will be summarised by means of descriptive statistics.

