#### AEs

- The list of PTs defining the solicited AEs has been expanded.
- Treatment-emergent AEs (TEAEs) have been redefined to exclude AEs with a start day more than 7 days after last IMP administration. In addition, the term non-TEAE has been introduced and specified.

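### The SAP nests IMP-related AEs, and the SAE and special-interest summaries, inside a 7-day post-treatment window, so later events reach the listing but not the TEAE-based summaries by arm

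*SAP*

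**What the plan says.** SAP 4.5.2 gives this definition of a TEAE: "AEs with start time on or after the time of first IMP administration and no later than 7 days after the last day of IMP". Anything starting later is a non-TEAE. The same section builds three further items on that definition:

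- Related events: "IMP-related AEs are TEAEs that are assessed 'possibly related' or with missing assessment".
- Special interest: "Number of events and number and percentage of subjects having TEAEs of special interest will be displayed in summary tables".
- Serious events: "TEAEs leading to IMP interruptions, serious TEAEs (SAEs) and TEAEs leading to IMP discontinuations will be summarised by SOC, PT and treatment group".

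SAP 4.5.2 also says that all AEs, including non-TEAEs, are listed, and that an event whose timing is in doubt because of partial dates counts as treatment-emergent.

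The protocol is wider. Section 15.9 says that, unless otherwise specified, "AE endpoints in this protocol refer to events occurring after the first IMP administration (treatment-emergent AEs"), with no end point relative to the last dose. Section 2.7 names IMP-related AEs as an endpoint of their own, without the treatment-emergent qualifier. Section 12 requires AEs to be recorded from consent to the last follow-up phone contact.

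SAP 4.8 declares the change: "Treatment-emergent AEs (TEAEs) have been redefined to exclude AEs with a start day more than 7 days after last IMP administration". It gives no reason for choosing 7 days and does not mention that the category of IMP-related AEs becomes narrower as a result.

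**The concern.** Whether an AE is related to IMP is a judgement that protocol 12 and 12.2 assign to the investigator, a physician. Under the SAP a calendar rule comes first. An event that the investigator judged possibly related, with onset on day 8 after the last tablet, is by definition not an IMP-related AE.

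A window on TEAEs is a common way to keep routine tables focused on treatment. Applying the same window to events already judged related has a different effect, because the causality assessment is then ignored for a named safety endpoint. Relative to the protocol definition, the rule can leave counts of related AEs, SAEs and special-interest events unchanged or lower them; it cannot raise them. What is lost is the comparison by arm, since a listing shows the cases but does not tabulate them against the numbers treated.

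The time outside the window is followed deliberately. The flow chart has a follow-up call after V11, and protocol 5.1 says that subjects taken off IMP for the listed reasons should remain for safety assessments.

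**Working it through.** The plan states no figure that can be reproduced here. The check compares the definitions and then sizes the excluded time.

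**Definitions, for an event that starts 8 days after the last tablet and is judged possibly related**

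| Question | Protocol | SAP 4.5.2 |
|---|---|---|
| Treatment-emergent? | Yes (15.9: after first IMP) | No (after day 7) |
| IMP-related AE? | Yes (2.7, 12.2: causality) | No (not a TEAE) |
| In the SAE summary, if serious? | Yes | No (serious TEAEs only) |
| In the special-interest summary, if of that type? | Not specified in 15.9 | No (TEAEs only) |
| In the listing? | Not specified in 15.9 | Yes |

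**Inputs**

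- Randomised: 533 (SAP 1.2).
- Stopped IMP but did not withdraw at that time: 3 (SAP 1.1.9.3).
- Planned treatment: 24 to 30 months (protocol 3.1 and 3.2).
- TC21: V11 + 2 weeks, window +7 days, so day 14 to 21 (flow chart in both documents). The V11 entry in the protocol visit schedule (Table 6) instead says about one week later.
- Assumptions: last tablet at V11; every randomised subject reaches V11 and TC21; no dropout in the denominator; each of the 3 subjects off IMP for as long as 30 months, which is deliberately too long.

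**Completers, per subject**

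Days outside the window = TC21 day − 7.

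- Day 14: 14 − 7 = 7 days.
- Day 21: 21 − 7 = 14 days.
- Call at about day 7: 7 − 7 = about 0 days.

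**Person-years outside the window (subjects × days / 365)**

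- TC21 at day 14: 533 × 7 / 365 = 10.2.
- TC21 at day 21: 533 × 14 / 365 = 20.4.
- The 3 subjects: at most 3 × 30 / 12 = 7.5. They are 3 / 533 = 0.56% of those randomised.

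**Share of planned treatment time**

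- Planned person-years: 533 × 24 / 12 = 1066 to 533 × 30 / 12 = 1332.5.
- Low end, TC21 at day 14 and completers only: 10.2 / 1332.5 = 0.8%.
- High end, TC21 at day 21 plus the 3 subjects: (20.4 + 7.5) / 1066 = 2.6%.
- Call at about one week, the 3 subjects only: at most 7.5 / 1066 = 0.7%.

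These figures give the scale and are not strict bounds. Dropout would change numerator and denominator. Subjects who withdrew early may have had a final visit and TC21 where possible (protocol 5.2), with an unknown gap since their last tablet. A missing last-dose date is imputed as the date of last contact (SAP 7.1.4), which lengthens the window for those subjects.

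**The case against.** There is a fair case that this matters little.

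- **Late events stay in the report.** All AEs are listed, special-interest classification and reporting within 24 hours are untouched, and missing causality counts as related. A reader might infer that late events vanish from all safety output. The documents do not support that: laboratory, vital-sign and lung-function tables do not depend on the window, and the wording for medication error, abuse, misuse and overdose is not clearly limited to TEAEs.
- **The change is disclosed.** SAP 4.8 declares the redefinition and describes several special-interest summaries as treatment-emergent. The SAP says that it was approved before database lock and unblinding, and protocol 15.9 leaves further AE detail to the SAP. The protocol's serious-event endpoint is itself worded as treatment-emergent, although 15.9 gives that term no upper limit.
- **Few subjects stayed on after stopping IMP.** The group kept for safety under protocol 5.1 amounts to 3 subjects by the SAP's own count.
- **No skew between arms is shown.** It is tempting to infer that the rule mainly favours the active arm. No figure in the documents supports this, and for completers, who supply most of the affected time if the flow-chart timing applies, there is no stated reason for imbalance.
- **Eosinophilic oesophagitis is a weaker example than it looks.** Protocol 5.1 lists as a reason for stopping IMP: "The subject experiences severe or persistent symptoms of oesophagitis". One might infer that a later diagnosis would often fall after day 7. But such symptoms would normally have begun on treatment, protocol 12.3 asks for one AE form from start to resolution with the diagnosis where available, doubtful dates count as treatment-emergent, and partial start dates are imputed early (SAP 7.1.4). It is also an event of special interest and not one of the endpoints listed in protocol 2.7.

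All of this stands, and it limits the size of the point. It does not answer the definitional problem: an event that the investigator judged possibly related is not counted as IMP-related because of its date, and SAP 4.8 neither explains this nor mentions it.

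**Conclusion.** The point holds as a limited defect in definition. Related AEs, SAEs and events of special interest that start more than 7 days after the last tablet appear only in the listing of all AEs and not in the TEAE-based summaries by arm, which is narrower than protocol 15.9 and 2.7.

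The excluded follow-up is about 0.8% to 2.6% of planned treatment time if TC21 follows the flow chart, and at most about 0.7% if the call is about one week after V11, under the assumptions stated above. How many events fall there, and in which arm, cannot be known from the documents. Nothing here shows that the safety conclusions would change. The case for acting is that the gap concerns a named safety endpoint in a paediatric trial and costs little to close.

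**What to change.** In SAP 4.5.2:

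1. Keep the TEAE window, "no later than 7 days after the last day of IMP administration", for the routine tables.
2. Define IMP-related AEs as all AEs with onset on or after first IMP that are assessed as possibly related or have no assessment, whatever the time since last IMP.
3. Add one summary by arm of related AEs, SAEs (including deaths) and events of special interest with onset more than 7 days after last IMP.
4. In SAP 4.8, give the reason for 7 days and state how the window affects IMP-related AEs.

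Separately, the two TC21 timings (protocol flow chart and visit schedule) must be reconciled, because they determine how much follow-up lies outside the window.

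The cost is some SAP wording and one small table from data already in the eCRF. The downside for the sponsor is that counts of related AEs and reported SAEs may be slightly higher. If the SAP can no longer be amended before lock, the summary can still be produced, with the change documented in the trial report and any post-hoc analysis marked as such, as protocol section 15 requires.

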#### 4.5.3 Additional safety assessments

Vital signs, physical examination assessments, and laboratory assessments will be summarised by visit and treatment group.

The pulmonary function test parameters (FEV1, FVC, percentage predicted FEV1 and percentage predicted FVC) will be summarised by visit and treatment group.

Physical examination assessments will be presented as shift tables from baseline (visit 2) to the end-of-treatment visit (visit 11) and will be summarised by visit. Laboratory assessments will also be presented as shift tables from baseline (visit 1) to the end-of-treatment visit (visit 11).

Vital signs and FEV1 will be summarised by treatment as mean, SD, median, 5%-percentile and 95%-percentile minimum and maximum by visit.

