9.6 Post-trial treatment

After the end of the trial, the investigator must advise trial subjects on access to appropriate and available treatment. Such treatment will not be sponsored by ALK.

10 Visit schedule

In Table 6, the procedures that should be performed at each visit is described. The procedures are listed in the chronological order in which they should preferably be performed:

Visit ID	Procedures to be performed at the visit
Visit 1 (screening)	 Obtain written informed consent for the trial, storage of serum samples in the ALK Research Biobank, and for pharmacogenetic testing, before any other trial procedures are performed Obtain demographic data (sex, date of birth, race, ethnic origin) Record medical history Rhinoconjunctivitis and asthma medication history Evaluate previous asthma exacerbations Assess eosinophilic oesophagitis Record use of relevant concomitant medication Height and weight Measure vital signs Perform physical examination Measure FEV1 and calculate the % of predicted FEV1 after 6 hours of SABA washout Collect urine for pregnancy test if applicable (No data are available for SPT in pregnant subjects, therefore perform the urine pregnancy test before SPT) Perform SPT and evaluate results⁵⁴ (to be performed at visit 2, if wash-out of concomitant medication is required) Assess compliance with inclusion and exclusion criteria Collect blood and urine sample for safety laboratory assessments

Table 6Visit schedule

⁵⁴ If medication that could interfere with the skin prick test, according to Table 9, has not been washed out and the positive control is <3 mm for subjects in Europe and <5 mm for subjects in North America, the skin prick test must be repeated after the interfering medication has been washed out.

Visit ID	Procedures to be performed at the visit
	 Collect blood sample for specific IgE against D. pteronyssinus, D farinae, Cladosporium herbarum and Blattella germanica Assess AEs Schedule date for visit 2
TC1	 Inform subjects of continued participation in trial depending on the blood sample for specific IgE against D. pteronyssinus and D. farinae Assess AEs occurring since the last visit Evaluate asthma exacerbations occurring since the last visit Record changes to concomitant medication

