Visit 2 (baseline)	 Assess AEs occurring since the last visit Evaluate asthma exacerbations occurring since the last visit Assess eosinophilic oesophagitis Record changes to concomitant medication Re-assess compliance with inclusion and exclusion criteria Perform oropharyngeal examination Measure height and weight Measure vital signs Measure FEV1 and calculate the % of predicted FEV1 after 6 hours of SABA washout Collect urine for pregnancy test (if applicable) SPT, if not possible at visit 1 due to necessary wash-out of concomitant medication Evaluate inhalation technique Instruct the subject and/or parent/caregiver on how to use the asthma and rhinoconjunctivitis rescue medication Dispense asthma and rhinoconjunctivitis rescue medication Show Trial Video Issue and instruct the subject and/or their parent/caregiver in the use of the Asthma Action Plan. Dispense Peak Expiratory Flow (PEF) Meter Instruct the subject and/or their parent/caregiver in the use of rescue medication for severe allergic reaction (adrenaline/epinephrine auto-injector) in countries where this is a regulatory requirement Issue and instruct the subject and/or their parent/caregiver in the use of the Local and Systemic Allergic Reaction Emergency Plan Issue and instruct the subject and/or their parent/caregiver in the use of the eDiary for the next 21 days Activate the eDiary Schedule date for visit 3
TC2	 Assess AEs occurring since the last visit Evaluate asthma exacerbations occurring since the last visit Record changes to concomitant medication

Visit ID	Procedures to be performed at the visit

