11.10 Physical examination

The physical examination should be performed by a physician and should be based on the following body systems see Table 7.

Table 7	Physical	examination
	i iiyoioui	CAULTINITATION 1

Body system	Minimum examinations to be completed
General appearance	Nutritional status, consciousness, skin colour and for children developmental status
Skin	Inspection of skin
Head	Ears - Inspection of auricles and external canal (otoscopy is not required) Eyes - Inspection of conjunctivae and eyelids, examination of pupils including reaction to light Nose - Inspection of nasal mucosa (nasal endoscopy is optional) Oral cavity – oropharyngeal inspection of lips, tongue, tonsils and uvula will be performed for signs of mouth irritation, edema, and any other abnormalities. When performed at visit 3, it will take place before and 60 minutes after IMP administration.
Lymph nodes	Examination of lymph nodes (cervical, axillary, and inguinal lymph nodes)
Respiratory	Assessment of respiratory effort, including respiratory rate Palpation and percussion of chest Auscultation/stethoscopy of lungs
Heart	Auscultation/stethoscopy of the heart
Abdomen	It is up to the investigators discretion to evaluate whether an examination of the abdomen is necessary. Questions regarding symptoms may be sufficient.
Urogenital	It is up to the investigators discretion to evaluate whether an examination of the urogenital system is necessary. Questions regarding symptoms may be sufficient.
Musculoskeletal and neurological	It is up to the investigators discretion to evaluate whether an examination of the musculoskeletal/neurological system is necessary. Questions regarding symptoms may be sufficient.
Other abnormality	If applicable

Physical examination of optional body systems not performed should be marked as not done (ND) in the eCRF.

Significant findings that are present at screening must be recorded as medical history in the eCRF. Significant findings found at the following visits, which meet the definition of an AE, must be recorded on an AE page in the eCRF.

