#### Figure 2 Flow chart

Visit ID:	V1	TC1	V2	TC2	V3	V4	TC3, 4	V5	TC5, 6, 7	V6	TC8, 9, 10	V7	TC11, 12, 13	V8	TC14, 15, 16	V9	TC17, 18, 19	V10 	TC20 	V11 	TC21	UN
Visit:	Screen ing	Reten- tion	Base- line	Mid base- line call	Ran- domi- sation	Visit 4		Visit 5		Visit 6		Visit 7		Visit 8		Visit 9		Visit 10		Final visit	Follow -up	Un- sche- duled visit
Time  from randomisation (IMP initiation) for all visits and TCs, except for visit 11 (actual date of visit)	Max 12 wk before V3		- 3 wk - 7 d	- 2 wk ± 2 d	-	+ 4 wk + 7 d	+ 2m ±2d + 3m ±2d	+ 4m ± 7 d	+ 5m ±2d + 6m ±2d + 7m ±2d	+ 8m ± 7 d	+9m ±2d +10m ±2d +11m ±2d	+ 12m ± 7 d	+13m ±2d +14m ±2d +15m ±2d	+ 16m ± 7 d	+17m ±2d +18m ±2d +19m ±2d	+ 20m ± 7 d	+21m ±2d +22m ±2d +23m ±2d	+ 24m ± 7 d	2 wk prior to V11 ± 2 d	30 Apr ± 7 d	+ 2 wk from V11 + 7 d	
Informed consent and assent 	x																					
Demography	х																					
Medical history incl. evaluate previous asthma exacerbations	х																					
SPT 	х		(X)																			
Review of in-/exclusion criteria	х		х		х																	
Randomisation					х																	
Physical examination 	х																			х		(X)

<sup>1 Visit 10 is not applicable for subjects randomised in cohort 1 after 31-Mar-2018; for subjects randomised in cohort 2 after 31-Mar-2019, for subjects randomised in cohort 3 after 31-Mar-2020 and for subjects randomised in cohort 4 after 31-Mar-2022, if applicable.

<sup>2 TC20 performed 2 weeks prior to final visit.

<sup>3 Visit 11 will take place on 30-Apr-2020  $\pm$  7 days for cohort 1, 30-Apr-2021  $\pm$  7 days for cohort 2, 30-Apr-2022  $\pm$  7 days for cohort 3.

<sup>4 One month (m) is considered 30 days.

<sup>5 Obtain written informed consent for the trial, storage of serum samples in the ALK Research Biobank, and for pharmacogenetics testing, before any other trial procedures are performed.

<sup>6 If medication that could interfere with the SPT has not been washed out and the positive control is <3 mm for subjects in Europe or < 5 mm for subjects in North America, the SPT must be repeated after the interfering medication has been washed out.

 Oropharyngeal examination is included in physical examination

															Ũ	79						

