### 4.1 General considerations

If nothing else is mentioned, all the statistical tests described in this section use a significance level of 5% and all tests and confidence intervals are 2-sided. The null hypothesis is the hypothesis of no difference and the alternative to the null hypothesis is the hypothesis of difference.

Descriptive statistics for numerical variables include summary tables displaying mean, SD, median, minimum and maximum and relevant quantiles. Descriptive statistics for categorical variables include frequency tables that display numbers and percentage.

When age is used as fixed effect in the statistical models, it is the age assessed at randomisation that is used.

Type of document	Date:	11-Aug-2022	
Document ID	Version:	4.0	
	Status:	Final	
INTERNAL USE	Page:	29 of 79	

If baseline measurements are missing for any efficacy endpoints, the last measurement before or on the date of first treatment will be used, if possible, for the given endpoint (screening observation carried forward).

In addition, all efficacy endpoints will be presented in summary tables.

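### SAP 4.5.3 takes visit 2 as baseline for the physical-examination shift tables, but the full physical examination is scheduled at visit 1, not visit 2

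*SAP*

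**What the plan says.** SAP section 4.5.3 sets the two ends of the table: "Physical examination assessments will be presented as shift tables from baseline (visit 2) to the end-of-treatment visit (visit 11"). The sentence adds that results will be summarised by visit, and the section opens by promising summaries by visit and treatment group.

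The sentence that follows deals with the laboratory data and uses a different baseline: "Laboratory assessments will also be presented as shift tables from baseline (visit 1) to the end-of-treatment visit (visit 11").

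Physical examination is listed among the safety and tolerability endpoints in protocol section 2.7 and SAP section 1.1.7. Under SAP section 4.5, safety tables use the safety analysis set unless stated otherwise.

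On scheduling, the protocol's Table 6 (section 10) lists "Perform physical examination" at visit 1 and again at visit 11. At visit 2 it lists "Perform oropharyngeal examination". A footnote to the SAP flow chart (Figure 2) explains how the two relate: "Oropharyngeal examination is included in physical examination".

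**The concern.** A shift table cross-classifies each subject's baseline result against the later result, so both must have been collected. Here the visit named as baseline has no scheduled full examination. A programmer following the SAP to the letter would find baseline values for one part of the examination and none for the rest.

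What is at stake is the only within-subject comparison with baseline that the SAP specifies for this safety endpoint. It would be lost for nearly every item, including minor changes that are neither clinically significant nor reportable as adverse events. The other possibility is that someone substitutes visit 1 informally, and the output then departs from the SAP without a record.

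**Working it through.** The plan gives no figure to reproduce here. The check compares the schedule with the analysis rule.

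**Step 1: when each assessment is scheduled** (protocol Table 1 and SAP Figure 2, which agree).

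| Assessment | Scheduled visits | Optional |
|---|---|---|
| Physical examination | V1, V11 | Unscheduled visits |
| Oropharyngeal examination | V2 to V10 | Unscheduled visits |
| Safety laboratory | V1, V7, V11 | Unscheduled visits |

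Protocol Table 6 agrees for visits 1, 2 and 11. Full physical examinations scheduled at visit 2: none.

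**Step 2: what the visit 2 examination covers.** Protocol Table 7 describes the oral-cavity part as "oropharyngeal inspection of lips, tongue, tonsils and uvula". It is one of four items in the Head row, beside ears, eyes and nose.

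- Table 7 has 10 rows. Counting Head as its four items gives 9 + 4 = 13 items.
- Items with a scheduled visit 2 value: 1 (oral cavity).
- Items without one: 13 − 1 = 12.
- Of these 12, three are at the investigator's discretion (abdomen, urogenital, musculoskeletal/neurological) and one applies only if relevant (other abnormality). That leaves 12 − 4 = 8 routinely examined items with no visit 2 value: general appearance, skin, ears, eyes, nose, lymph nodes, respiratory and heart.

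**Step 3: whether another rule supplies the baseline.** SAP section 4.1 has a fallback: "If baseline measurements are missing for any efficacy endpoints, the last measurement before or on the date of first treatment will be used". It is confined to efficacy endpoints, and physical examination is a safety endpoint. SAP section 4.8, which records changes from the protocol, mentions no change to the examination schedule or its baseline. An optional examination at an unscheduled visit is not a visit 2 value.

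**Step 4: what the documents treat as the reference examination.** Protocol section 11.10 points to screening, which is visit 1: "Significant findings that are present at screening must be recorded as medical history in the eCRF". The laboratory sentence in SAP 4.5.3 also uses visit 1, and that matches the laboratory schedule in Step 1.

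**Step 5: the table with visit 1 as baseline.** Both ends, V1 and V11, then have a scheduled full examination. The oral cavity is covered at both, because the full examination includes it.

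**The case against.** The best defence is that this is a slip of labelling with little consequence. The flow chart calls visit 2 the baseline visit, which probably explains the number. Protocol section 15.9 asks only for descriptive statistics on physical examination, so the shift table is an addition made by the SAP. The visit 1 data exist, and any programmer would notice the gap. All of that stands and limits the weight of the point. It does not make the sentence correct.

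A reader might go further and infer that a new abnormality at visit 11 could not be told apart from one already present at screening. The documents do not support that. Under protocol section 11.10, significant screening findings go to medical history, and later significant findings that meet the definition go on an adverse event page. Protocol section 12.1 keeps documented pre-existing conditions out of the adverse events unless they worsen. The SAP summarises both sources by treatment group (sections 4.5.2 and 6.3). The by-visit summaries in 4.5.3 also show visit 1 and visit 11 results at group level.

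A reader might also attach the figure of 533 subjects. That is the number randomised (SAP section 1.2). The tables use the safety analysis set, which requires at least one dose and whose size the documents do not give. Only subjects with a visit 11 examination can contribute a shift to that visit.

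**Conclusion.** The inconsistency is real, and the sentence is wrong as written. With visit 2 as baseline, the shift tables for the safety analysis set have a scheduled baseline value for the oral cavity alone. The other 12 of the 13 Table 7 items, 8 of them routinely examined, have none.

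The size is minor. The loss is the within-subject tabulation of shifts in one set of descriptive safety tables. Detection of significant new findings does not depend on it, and there is no effect on efficacy, alpha or sample size.

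The conclusion assumes that examinations followed the schedule. Some entries for the discretionary systems may be missing whichever visit is used, because those systems can be marked as not done.

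**What to change.** In SAP section 4.5.3, change the baseline for the physical-examination shift tables from visit 2 to visit 1. The laboratory sentence is already right and stays as it is.

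No separate baseline for the oral cavity is needed. A reader might think of using the pre-dose examination at visit 3, but the visit 1 examination already contains the oropharyngeal part, and a second baseline would mix two reference visits in one table.

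The cost is one visit number in the SAP, using data already collected. If the SAP is not amended, the use of visit 1 should be documented in the integrated clinical trial report, as protocol section 15 requires for departures from the final SAP.
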